contributor to mortality (5, 6). It has been reported that children with DS exhibited a significantly higher number of signs and symptoms of autonomic nervous system abnormalities than children in a control group (7). Studies of electrical and autonomic cardiac function in patients with DS demonstrated an imbalance of cardiac autonomic function toward a relative predominance of adrenergic tone compared to both healthy children and patients with other forms of epilepsy, and this finding was independent of the use of antiepileptic medications (8, 9). This suggests that dysfunction in the autonomic nervous system, or dysautonomia, is a significant factor in this condition. A number of these patients have seizures triggered by autonomic stimulation (e.g., strong emotion), and many have pronounced autonomic features (e.g., flushing of face, pallor or tachycardia) during ictal events. Modulating autonomic nervous system tone may potentially affect seizure control and risk for SUDEP.

Investigators have been unable to accurately determine the incidence of SUDEP in patients with LGS, perhaps due to variation in the etiology and definition of LGS. In addition, the literature available on LGS and autonomic nervous system dysfunction is sparse, as is the literature on LGS and cardiac function. Patients with LGS may be at an increased risk for cardiac abnormalities (10). Nei (2012) documented sinus-tachycardia, T wave inversion and ST segment depression during tonic seizures, as well as 3 to 4.8 seconds of asystole during sleep in subjects wearing a subcutaneously implanted loop recorder (10). Studies of SUDEP have identified increased risk in those with early onset and medically intractable epilepsy, neurologic abnormalities, and a need for multiple medications. Children with LGS meet all these criteria.

Available antiepileptic drugs (AEDs) have not proven to be particularly effective in offering seizure control to those with severe pediatric epileptic encephalopathies. Recently, the use of cannabidiol (CBD) has generated great interest as a novel treatment for highly refractory epilepsy such as DS or LGS. Preliminary studies suggest that CBD may be effective in treating the seizures associated with DS. Major phase III drug trials of FDA-approved orphan drug products are close to implementation or are in the initial phase of recruitment. Families are also seeking out CBD products to use on their own through state-licensed pharmacies (e.g., through the state of Minnesota or www.epilepsycolorado.org).

Thus, a significant number of children with DS and LGS will soon be enrolling in stage III clinical trials or using CBD acquired as an artisanal oil. However, a number of questions regarding the safety and efficacy of CBD for treating seizures remain unanswered since FDA approval and labeling have not yet been granted. In addition, current phase III studies do not address potential autonomic adverse effects. While information on adverse effects may be

forthcoming in the future for industry-manufactured products, the existence of state-licensed pharmacies that currently dispense CBD as an artisanal oil creates an urgency to address these questions. The purpose of this protocol is to determine whether CBD affects cardiac autonomic function, which may pose another mechanism of action for seizure reduction and prevention of SUDEP.

To date, there is no medical literature that has determined whether CBD has cardiac autonomic effects on pediatric patients using CBD for neurological disorders including epilepsy. Several previous studies only suggest that CBD may modulate cardiac autonomic effects. One preclinical study reported that CBD attenuates cardiac responses to restraint stress in rats (11). In adult humans, CBD has been shown to attenuate anxiety (12). It has also been demonstrated in healthy adult volunteers that while an acute dose of the more well-known cannabinoid delta-9-tetrahydrocannabinol (THC) increases heart rate, CBD does not, suggesting that CBD may not result in deleterious adverse effects (13). These findings indicate the importance of characterizing the cardiac autonomic effects of CBD in pediatric patients with medically refractory epilepsy. If CBD modulates cardiac autonomic effects, it may also reduce the risk of SUDEP.

Summary of Background
DS and LGS are severe forms of epilepsy that are largely unresponsive to current AEDs
SUDEP is a major cause of mortality with intractable forms of epilepsy such as DS and LGS
Dysautonomia and increased risk for cardiac abnormalities may play a role in causing SUDEP in patients with highly refractory epilepsy
Modulating autonomic nervous system tone may affect seizure control and risk for SUDEP
Cannabidiol may have an effect on the autonomic nervous system and is now being studied as a potential treatment for refractory epilepsy
Cannabidiol is being obtained from state-licensed pharmacies without having undergone study in clinical trials, and thus, has not been well-characterized
This study will determine if Cannabidiol obtained from state-licensed pharmacies has any effects on cardiac rhythm and reduction in seizures

Rationale for Conducting the Study

Although marijuana has been in use for centuries, CBD has not been well studied as an antiepileptic medication for use in children. Little is known about the autonomic effects of CBD in general, and virtually nothing is known about

the effects that CBD might have on the cardiac function of children with DS or other severe forms of epilepsy. Currently, industry sponsors are conducting studies of CBD in connection with clinical trials of their study drugs. However, similar studies of CBD when administered as an artisanal oil derived from other sources have not been reported.

We propose to study the effects of CBD on cardiac electrical function and the autonomic nervous system in children with DS and LGS, when the CBD was administered as an artisanal oil obtained through state dispensaries or other sources. Our intent is to begin to assess potential risks and benefits of this therapy in a vulnerable patient population by characterizing the effects of CBD on EKG findings, heart rate variability and the occurrence of seizures.

Specific Aims/Study Objectives

This is a pilot study to explore the effects of cannabidiol (CBD) on autonomic cardiac function in children with DS or LGS when the CBD was administered as an artisanal oil. This will be achieved by addressing the following specific aims.

Aim #1: To determine the effects of CBD on cardiac function in 30 children with DS and LGS. This is the primary aim of the study: The effects of CBD on the cardiac function of 30 children with DS or LGS will be assessed using a 12-lead electrocardiogram (EKG), an optional signal average EKG, and a 24-hour Holter monitor. We hypothesize that there will be no alterations in ventricular repolarization and heart rate variability on the EKGs and Holter monitoring, respectively, after taking CBD for 4-8 weeks, compared to when participants were not taking CBD. *Milestone: Records from 12-lead EKG and 24-hour Holter monitor in 30 patients.*

Note: The following aims are secondary to the primary outcome and goal of assessing the effects of CBD on cardiac function.

Aim #2: To assess signs and symptoms of dysautonomia in the presence and absence of CBD. Signs and symptoms of dysautonomia include parental perception of body temperature, skin color in hands and feet, sweating, pupil size, flushing, feeding issues, heart rate, and constipation. These signs and symptoms will be collected using a previously-established dysautonomia survey. We hypothesize there will be no change in qualitative assessments of signs and symptoms of dysautonomia after taking CBD for 4-8 weeks, compared to when participants were not taking CBD. *Milestone: Completed dysautonomia surveys in 30 patients before and after CBD administration.*

Aim #3: To determine the effects of CBD on the occurrence of seizures. The number of seizures in children who obtain CBD will be assessed using a 7-day seizure diary (Seizure tracker). Caregivers will record the number of

seizures for a 7-day period prior to CBD administration, and repeat the seizure tracking after having received CBD for 4-8 weeks. Change in seizure numbers will be compared pre- and post-CBD administration. We hypothesize that study participants will have lower seizure counts after being on CBD compared to when weren't taking CBD. *Milestone: Completed 7-day seizure diaries in 30 patients before and after CBD administration.*

Study Design and Methodology

[figure not shown]
Study Design: Thirty patients with DS or LGS who are going to register to take medical cannabis (cannabidiol, or CBD) in the state of Minnesota will be offered the opportunity to participate in this study. If consent is obtained, the patient or guardian will be asked to complete a questionnaire developed for this study that documents observable signs and symptoms of dysautonomia, and to complete a seizure diary for 7 days prior to initially receiving the CBD. Each participant will also have a 12-lead electrocardiogram (EKG), an optional signal average EKG, and wear a 24-hour Holter monitor, all non-invasive measures of cardiac function, prior to being administered the CBD. The EKGs and 24-hour Holter monitor will be interpreted by a cardiac electrophysiologist and will be reviewed for heart rate variability parameters. The dysautonomia questionnaire, seizure diary and cardiac measurements will be repeated 4-8 weeks after the subject has been on a stable regimen of CBD. This time-frame is based on availability of subjects schedules and clinic visits, and it is also greater than 5 half-lives previously reported for CBD (apparent half-life, 21 hours, (15)). Steady-state levels are achieved after 5 half-lives of drug dosing, thus we expect to be at steady-state concentrations.

Subjects who are already on a stable regimen of CBD, yet plan to stop taking CBD at some point for some reason, are also eligible to participate. The patient or guardian will complete the dysautonomia questionnaire and seizure diary (and research staff will be available to help with questions), and the patient will have the 12-lead EKG, an optional signal average EKG, and 24-hour Holter monitor while still on the CBD. The subjects will then come back 4-8 weeks after their last dose of CBD to have these assessments repeated while off of the CBD. Again, this time frame is based on availability of subjects schedules and clinic visits as well as being substantially greater than 5 half-lives of CBD, the standard wash-out period for pharmacological studies.

Sample Size: A power analysis was not used to determine sample size. Current sample size expectations will be 40 subjects based on the number of patients who enroll in the Minnesota state registry and who are also patients at Gillette. This available sample size will allow us to account for potential participant dropout or incomplete data so that we can achieve our target of 30

patients. This is a pilot study with a limited number of participants, and data collected will be used in a subsequent power analysis to determine the number of subjects needed in a larger study to determine statistical significance. This will be the first study of medical cannabis' effects on autonomic function in children with severe seizures, and due to the anticipated small sample size, these findings will primarily be used as pilot data to guide further characterization of CBD effects on autonomic parameters.

Methodologies: The 12-lead EKG will be used to collect information on rhythm, a detailed assessment of heart rate (RR interval), PR interval, QRS duration, QT and QTc interval, and ST segment changes in order to detect cardiac arrhythmias and other abnormalities (see graphic below). The signal average EKG will take this same information and average them during a 20 minute time period, provided our subject is able to lie still for that amount of time.

Heart rate variability (HRV) will be assessed using the 24-hour Holter ECG recordings. Both time-domain parameters (RR interval [heart rate], SDNN [standard deviation of RR intervals] and SDNN-I [the mean of standard deviation of all RR intervals for all 5 minute segments]) and frequency-domain parameters (VLF [total spectral power of all NN intervals between 0.003 and 0.04Hz], HF [total spectral power of all NN intervals between 0.15 and 0.4Hz] and LF [total spectral power of all NN intervals between 0.04 and 0.15 Hz] amplitude) will be obtained. HRV is a measure of sympathetic/parasympathetic cardiac autonomic balance, with lower HRV parameters indicating increased adrenergic tone.

Data Analysis: The number of participants (30 subjects) is small due to the limited number of patients available for enrollment into this specialized study. The study is an observational study with a cross-over design, where the patients will serve as their own controls. Primary assessments will include determination of any changes in EKG parameters and Holter heart rate variability parameters

pre- and post-treatment with CBD, as well as the percentage of items in the dysautonomia survey that changed and the number of seizures that occurred pre- and post-treatment with CBD. Appropriate data assessments will be performed to determine whether parametric or nonparametric analyses are the proper approach. Due to the small sample size and potentially highly variable or skewed data due to the complex patient population under investigation, we plan to normalize Holter heart rate variability parameters and EKG parameters and calculate change from “baseline” (off – CBD) to those collected while CBD is being administered at steady-state levels.

We also will compare reported seizure data collected from subjects who enrolled in the study prior to initiation of CBD to those who were already on CBD and then discontinued CBD use to determine if substantial differences are apparent in the two groups, since parent report may be biased. We will also confirm that EKG and Holter monitor data 4-8 weeks post-CBD (from patients who were on CBD but subsequently discontinued use) are not significantly different from baseline data acquired from patients with no previous CBD use, prior to combining all “off – CBD” as baseline values.

Study Participation

The Principal Investigator or research team members will identify subjects who have registered or plan to register with the State of Minnesota to take medical cannabis. Each participant will be in the study for approximately 2 months, and will need to visit Gillette twice. If subjects have not been on CBD, they will make one visit one week prior to starting CBD treatment and one visit after having been on CBD for 4-8 weeks. For subjects that are already on a stable regimen of CBD, yet plan to stop taking CBD at some point, their participation will last 4-8 weeks after their last dose.

Risks and Discomforts

EKG: There is no pain during an EKG; however, the EKG patches may be cold and removing the pads may make the skin red and sore. In some cases, the locations where the EKG patches are placed may need to be shaved.

24-hour Holter monitor: There is no pain during the use of a 24-hour Holter monitor; however, the patches may be cold and removing the pads may make the skin red and sore. In some cases, the locations where the patches are placed may need to be shaved.

Subject Protection

A consent form will be used to explain the risks and benefits of study participation to the subject in simple terms before the subject will be entered into

the study. The consent form contains a statement that the consent is freely given, that the subject is aware of the risks and benefits of entering the study, and that the subject is free to withdraw from the study at any time. The consent form will incorporate (or be accompanied by a separate document incorporating) wording that complies with relevant data protection and privacy legislation.

Written consent must be given by the subject and/or legal representative after the receipt of detailed information on the study and all questions have been resolved.

The Principal Investigator is responsible for ensuring that informed consent is obtained from each subject or legal representative, and for obtaining the appropriate signatures and dates on the informed consent document prior to the performance of any protocol procedures. The Investigator or research team member will provide each subject with a copy of the signed and dated consent form.

Confidentiality

The records of this study will be kept private. Extra precautions will be taken to preserve confidentiality. All identifiable information will be replaced with a code. A list linking the code and identifiable information will be kept separate from the data. All research data and records will be stored electronically on a secure network with encryption and/or password protection to help prevent unauthorized access to personal information. All paper records will be stored in a secured area. Study participation will be recorded in the subject's medical record. Study records and samples will be kept until all data have been monitored, analyzed and published.

Data Handling and Record Keeping

It is the Principal Investigator's responsibility to maintain essential study documents (protocol and protocol amendments, completed eCRFs, signed informed consent forms, relevant correspondence, and all other supporting documentation). Record retention will follow ICH E6 Section 4.9.5 and all other applicable regulations.

Investigator Obligations

This study will be conducted in accordance with the ICH Harmonized Tripartite Guideline for GCP (GCP, 1997; the US CFR Title 21 parts 50, 56, and 312) and the ethical principles that have their origin in the Declaration of Helsinki.

The Principal Investigator agrees to conduct the clinical study in compliance with this protocol after the approval of the protocol by the IRB/IEC in compliance with local regulatory requirements.

Data and Safety Monitoring Plan

Data will be monitored by the Principal Investigator. All EKGs and 24-hour Holter monitors will be read by a cardiac electrophysiologist.

Clinical Implications and Dissemination

As described above, this is a pilot study with a limited number of participants and data collected will be used in a subsequent power analysis to determine the number of subjects needed in a larger study to determine statistical significance. This will be the first report of medical cannabis' effects on autonomic function in children with severe seizures, and due to the anticipated small sample size, these findings will primarily be used as pilot data to guide further characterization of CBD effects on autonomic parameters. Findings will be reported internally and at external conferences, likely the annual American Epilepsy Society meeting. Data regarding the effects of CBD on cardiac function (whether protective or detrimental) will be important for future development and use of CBD in clinical settings with patients with potential cardiac dysfunction.

Bibliography

2. <http://www.ninds.nih.gov/disorders/lennoxgastautsyndrome/lennoxgastautsyndrome.htm>, Retrieved 6.10.2015
5. Jehi L. Sudden death in epilepsy, surgery, and seizure outcomes: the interface between heart and brain. *Cleve Clin J Med*. 2010 Jul;77 Suppl 3:S51-5. doi: 10.3949/ccjm.77.s3.09. Review. PMID: 20622077

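### The aims name 4-8 weeks on CBD, but children who stop CBD may have used it for any unstated time, and no EKG/Holter or survey step compares their change with that of starters

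*Combined protocol and SAP*

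**What the plan says.** All references are to the combined protocol and SAP.

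- **Specific Aims/Study Objectives.** Aim 1, the primary aim, hypothesises no alteration in repolarisation or heart rate variability "after taking CBD for 4-8 weeks, compared to when participants were not taking CBD". Aim 2 expects no change in "signs and symptoms of dysautonomia after taking CBD for 4-8 weeks". Under Aim 3, caregivers "repeat the seizure tracking after having received CBD for 4-8 weeks", although the Aim 3 hypothesis names no duration: "study participants will have lower seizure counts after being on CBD".
- **Study Design, starters.** The off-CBD assessments come first and are "repeated 4-8 weeks after the subject has been on a stable regimen of CBD". Study Participation describes the same visit as "one visit after having been on CBD for 4-8 weeks".
- **Study Design, stoppers.** Also eligible are "Subjects who are already on a stable regimen of CBD, yet plan to stop taking CBD at some point for some reason". A stable regimen is not defined, and no minimum or maximum prior use is given. These children are assessed while on CBD and again 4-8 weeks after the last dose.
- **Data Analysis.** The plan calculates change from off-CBD baseline to values under CBD at steady state, with no duration attached. For EKG and Holter data it first confirms that the stoppers' off-CBD values do not differ significantly from those of never-users, "prior to combining all “off – CBD” as baseline values". Reported seizure data are compared between the cohorts because parent report may be biased. No cohort comparison is described for the dysautonomia survey.

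**The concern.** In starters, 4-8 weeks is time on the drug. In stoppers it is time off the drug, and their on-CBD recording may follow weeks, months or years of use. Only by coincidence does a stopper supply the exposure that the aims name. Stoppers are also leaving CBD for a reason that the plan leaves open.

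The EKG/Holter check cannot reveal a difference in effect. Equal off-CBD values in the two cohorts say nothing about whether the change on CBD is equal.

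Two uses of the results are exposed. First, a combined finding of no alteration could be reported as applying to 4-8 weeks of CBD. Because the primary hypothesis is one of no change, a smaller change in stoppers would move the combined estimate towards that hypothesis. Second, Sample Size and Clinical Implications both say that the data will feed the power analysis for a larger study. A mean and SD taken across two contrasts may not suit a study of either one.

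**Working it through.** **1. The plan's own timing figure.** Study Design gives an apparent half-life of 21 hours and says that 4-8 weeks exceeds five half-lives.

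- 5 × 21 h = 105 h, and 105/24 = 4.4 days. The fraction of steady state reached is 1 − 0.5^5 = 0.97.
- 4 weeks = 672 h, and 672/21 = 32 half-lives. 8 weeks = 1,344 h, or 64 half-lives.

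The claim reproduces. It also shows what steady state does not do. On a constant regimen it is reached in about 4.4 days, so requiring it does not confine the on-CBD recording to 4-8 weeks of use. It supports similar drug levels, not an equal autonomic response after weeks and after longer use. The Rationale section itself says that little is known about the autonomic effects of CBD.

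**2. The two cohorts side by side.**

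| | Starters | Stoppers |
|---|---|---|
| Order | off, then on | on, then off |
| Time on CBD at on-visit | 4-8 weeks, counted from a stable regimen or from being on CBD | stable regimen, duration not limited |
| What 4-8 weeks measures | time on CBD | time since last dose |
| Fits the wording of Aims 1 and 2 | yes, if counted from first use | only by coincidence |

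**3. What a combined mean would estimate.** Let d₁ be the mean on-minus-off change in starters, d₂ that in stoppers, and p the share of stoppers. Then:

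pooled mean = (1 − p)d₁ + p·d₂, so pooled − d₁ = p(d₂ − d₁).

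The documents give none of p, d₁ and d₂. For illustration, assume 5, 10 or 15 stoppers among the target of 30 and write r = d₂/d₁. The ratio of pooled to starters' change is (1 − p) + p·r:

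| Stoppers of 30 | p | r = 0 | r = 0.5 | r = 1 | r = 1.5 | r = 2 |
|---|---|---|---|---|---|---|
| 5 | 0.167 | 0.83 | 0.92 | 1.00 | 1.08 | 1.17 |
| 10 | 0.333 | 0.67 | 0.83 | 1.00 | 1.17 | 1.33 |
| 15 | 0.500 | 0.50 | 0.75 | 1.00 | 1.25 | 1.50 |

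At r = 1 there is no distortion. The ratio is undefined if starters have no change, but the difference form still applies: with d₁ = 0 the pooled mean is p·d₂, that is 0.17, 0.33 or 0.50 of the stoppers' change.

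**4. What the existing check can show.** It tests off-CBD values, not the change. It is also weak for its own purpose. By normal approximation, two-sided 0.05, a true cohort difference of 0.5 SD in off-CBD values is detected with power 17% (25 starters, 5 stoppers), 25% (20, 10) or 28% (15, 15).

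**The case against.** The strongest reply is that 4-8 weeks is a visit window and not the quantity of interest. Study Design ties it to scheduling and to exceeding five half-lives. Data Analysis sets steady-state CBD against off-CBD without a duration, Aim 2 opens with the presence and absence of CBD, and the Aim 3 hypothesis names no length of use. On this reading, stoppers on a stable regimen meet the intended condition and the aims were simply not reworded for the second cohort. Much of this stands. It is why rewording the aims is a sufficient repair and a starters-only headline is not required. It does not remove the mismatch: the hypotheses of Aims 1 and 2 still state a duration, and nothing planned would show whether the EKG/Holter or survey change differs between cohorts.

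Four stronger readings are tempting, and the documents do not support them.

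- *All outcomes are pooled by plan.* Combining is explicit only for off-CBD EKG/Holter values, and only after the check. For the survey and seizures it is inferred from the single pre/post analysis and the common target of 30.
- *The plan never compares the cohorts.* It does so for seizure data, though the stated reason is reporting bias and not duration.
- *Stoppers may enter in any state of use.* They must be on a stable regimen; what is missing is a definition and a duration limit.
- *Starters cleanly supply the 4-8 week exposure.* If the interval runs from a stable regimen, as Study Design says, their total time on CBD may exceed 8 weeks.

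**Conclusion.** The concern holds as a mismatch between the exposure named in the aims and the exposures that the design admits, with no planned step that would show whether it matters for the primary EKG/Holter outcomes or the survey. It should be corrected.

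A reader might infer that the combined estimate is biased, or that the wrong quantity is being analysed. The documents do not show either. If the response does not depend on duration or cohort, pooling distorts nothing. The size of any distortion cannot be calculated without the cohort split and the prior durations. The table above is arithmetic on assumed values: across r from 0.5 to 2 it runs from 0.92-1.17 of the starters' change with 5 stoppers to 0.75-1.50 with 15. The mismatch itself does not depend on those assumptions.

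**What to change.** 1. Record the CBD start date, and hence time on CBD at the on-CBD visit, for every child.
2. For EKG/Holter, survey and seizure outcomes, report the within-child on-minus-off change and its SD separately for starters and stoppers. Give the between-cohort difference with its confidence interval, beside the pooled change. Carry the cohort-specific SDs into the later power analysis.
3. Reword the aims as CBD at steady state versus off CBD, naming both contrasts. Keep the label of 4-8 weeks on CBD for starters only.
4. Reconcile Study Design, which counts the starters' 4-8 weeks from a stable regimen, with Study Participation, which counts it from being on CBD.

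A starters-only headline is optional. Under the assumed splits it would rest on 25, 20 or 15 of 30 children.

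The cost is one data field, some wording and a few extra table rows. Recruitment, visits and treatment do not change. The cohort-specific estimates will be imprecise: the 95% half-width for the between-cohort difference, 1.96 × √(1/n₁ + 1/n₂) in units of a common SD of change, is 0.96 for 25/5, 0.76 for 20/10 and 0.72 for 15/15. The comparison is therefore descriptive. A difference, if seen, could reflect duration or the kind of child who stops, and the data would not separate the two.

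### HF power stops at 0.4 Hz (24 breaths per minute) for every child and no beat-to-beat measure stands beside it, so a change in breathing rate can look like an autonomic change

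*Combined protocol and SAP*

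**What the plan says.** All references are to the combined protocol and SAP, section Study Design and Methodology, unless stated otherwise.

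- **Source of the data (Methodologies).** "Heart rate variability (HRV) will be assessed using the 24-hour Holter ECG recordings". Waking and sleep are therefore both covered.
- **Time-domain set.** Three measures are named: the RR interval, its overall standard deviation (SDNN), and a version built from short segments, "SDNN-I [the mean of standard deviation of all RR intervals for all 5 minute segments". No measure based on differences between successive beats, such as RMSSD or pNN50, is listed.
- **Frequency-domain set.** Three bands are named. VLF runs from 0.003 to 0.04 Hz and LF from 0.04 to 0.15 Hz; the remaining one is "HF [total spectral power of all NN intervals between 0.15 and 0.4Hz". The bands are the same for every participant.
- **Reading rule.** HRV is taken as an index of autonomic balance, "with lower HRV parameters indicating increased adrenergic tone".
- **Population (Specific Aims, Aim #1).** "To determine the effects of CBD on cardiac function in 30 children with DS and LGS". The available text gives no age range and no breathing rates.
- **Analysis (Data Analysis).** Each child's on-CBD values are compared with that child's off-CBD values after a normalization that is not defined. Breathing rate is not mentioned. Under Aim #1 the hypothesis is that HRV does not change.

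**The concern.** Breathing produces an oscillation in the RR interval at the breathing frequency. Of the listed parameters, only HF is placed to isolate it. SDNN and SDNN-I contain it but mix it with slower variation. VLF and LF lie below 0.15 Hz, or 9 cycles per minute.

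If a child breathes close to the upper edge of the HF band, part of the oscillation falls outside it, and the captured share depends on the breathing rate. When that rate differs between the two recordings, HF changes even though the underlying modulation is the same. Under the plan's reading rule, a fall in HF produced this way would be taken as more adrenergic tone on CBD. A shift in the other direction could offset a real fall and appear to support the no-change hypothesis. HRV belongs to the primary aim, and the pilot data are meant to feed the power analysis of a larger study, so a distorted HF mean or variance would carry forward.

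**Working it through.** **Inputs from the plan.** HF band 0.15 to 0.40 Hz, 24-hour recording, within-child comparison. The band edge is a definition, so there is no computed figure in the plan to reproduce.

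**Inputs assumed, because the documents give none.** Breathing rates of 14 to 30 per minute; a Gaussian respiratory peak with SD 0.05 Hz (range 0.03 to 0.08); total respiratory power constant; for a mixed day, 60% awake and 40% asleep with equal respiratory power per unit time in both states.

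**Step 1, band edges.** 0.15 × 60 = 9 and 0.40 × 60 = 24 cycles per minute.

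**Step 2, share of respiratory power inside the band.** With f = breaths per minute / 60,

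share = Φ((0.40 − f)/SD) − Φ((0.15 − f)/SD).

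| Breaths/min | SD 0.03 | SD 0.05 | SD 0.08 |
|---|---|---|---|
| 14 | 0.997 | 0.952 | 0.833 |
| 16 | 1.000 | 0.986 | 0.880 |
| 18 | 1.000 | 0.976 | 0.864 |
| 20 | 0.987 | 0.909 | 0.787 |
| 22 | 0.867 | 0.748 | 0.658 |
| 24 | 0.500 | 0.500 | 0.499 |
| 26 | 0.133 | 0.252 | 0.338 |
| 28 | 0.013 | 0.091 | 0.202 |
| 30 | 0.000 | 0.023 | 0.106 |

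**Step 3, one constant rate all day, no autonomic change.**
- 26 to 22 per minute: 0.748 / 0.252 = 3.0 (1.95 to 6.5 over the SD range).
- 22 to 26 per minute: HF falls by 66% (49% to 85%).
- 20 to 18 per minute: HF rises by 7% (1% to 10%).
- 18 to 16 per minute: HF rises by 1% (0% to 2%).

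**Step 4, mixed day, a fall of 4 breaths per minute throughout (SD 0.05).**
- Awake 26, asleep 20. Before: 0.6 × 0.252 + 0.4 × 0.909 = 0.515. After (22 and 16): 0.6 × 0.748 + 0.4 × 0.986 = 0.843. Ratio 1.64 (1.44 to 1.94 over the SD range).
- Awake 22, asleep 18. Before: 0.6 × 0.748 + 0.4 × 0.976 = 0.839. After (18 and 14): 0.6 × 0.976 + 0.4 × 0.952 = 0.966. Ratio 1.15.

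In reverse, a factor of 1.64 would hide a real fall in respiratory power of 1 − 1/1.64 = 39%, and a factor of 1.15 a real fall of 13%.

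**Step 5, check of the proposed additions.**
- *Wider band.* A beat-sampled series carries no information above half the heart rate: 100 / 60 / 2 = 0.83 Hz at 100 beats per minute, and 0.67 Hz at 80. A fixed edge of 1.0 Hz would exceed this limit at any heart rate below 120 (1.0 × 2 × 60). With an edge at 0.67 Hz, the share at 30 breaths per minute is about Φ((0.67 − 0.50)/0.05) = Φ(3.4), above 99.9%, so the dependence on breathing rate practically disappears in this model.
- *RMSSD.* For an oscillation of constant amplitude it is proportional to sin(π × f × RR). At 100 beats per minute RR = 0.6 s. At 26 breaths per minute, sin(π × 0.433 × 0.6) = 0.729; at 22, sin(π × 0.367 × 0.6) = 0.637. The ratio is 0.87, a fall of about 13%, opposite in direction to the rise in HF.

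**The case against.** The strongest objection is that the premise is not in the documents. The available text states neither ages nor breathing rates, and nothing in it says that CBD alters breathing. If the children breathe at about 18 per minute, 98% of the power is captured and the issue nearly vanishes. This stands, and it is why the point is conditional.

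The within-child comparison also helps: truncation that is equal at both recordings largely cancels in a relative change. It does so only if breathing rate is similar on both occasions, which the plan does not check.

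The 24-hour recording includes sleep, so the threefold change for a constant rate straddling the edge is an extreme illustration. The mixed-day ratios of 1.15 and 1.64 are fairer. HF is also one of six listed parameters, the plan never calls it a vagal index or the deciding measure, and SDNN and SDNN-I have no 0.4 Hz ceiling. All this stands, although those two cannot isolate breathing-linked variation.

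The remedy has limits too. RMSSD depends on breathing rate itself, and without a respiratory signal breathing and autonomic change cannot be fully separated. Because RMSSD moves the opposite way to HF in the example, it still works as a check.

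A reader might infer that HF misses the vagal signal in these children, or that an HF change in this study would be a breathing artefact. The documents do not support either. Under the model half the power is still captured at 24 breaths per minute and a quarter at 26. Near-total loss starts only at about 28 to 30, and whether any child breathes that fast for long is unknown.

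**Conclusion.** The point holds in conditional form and is an inexpensive improvement to a pilot study. The fixed 0.4 Hz edge can remove part of the breathing-linked power in children who breathe near or above about 22 to 24 per minute for part of the day. A difference in breathing rate between recordings can then change HF without any autonomic change, and no other listed parameter would reveal it.

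Under the model, a fall of 4 breaths per minute gives a factor of roughly 1.15 to 1.6 over a mixed day and 3.0 at worst among the cases worked at SD 0.05. The effect is small when breathing stays below about 20 per minute. These sizes rest on the assumed rates, peak width and day mix. The documents do not allow an estimate of how many children are affected, of the bias in this study, or even of whether a bias will occur.

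**What to change.** In the Methodologies paragraph:

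1. Add RMSSD (root mean square of successive NN differences) to the time-domain set.
2. Keep HF at 0.15-0.4 Hz, and report beside it a sensitivity value with a wider upper edge, capped at half the child's mean heart rate in Hz. Use the same edge for both of a child's recordings, set from the slower mean heart rate, so that the edge itself cannot create a difference.
3. State that a change in HF will be interpreted as autonomic only if RMSSD and the wider-band HF change in the same direction. Note that RMSSD also depends modestly on breathing rate, in the opposite direction, and that agreement in direction is a screen and not proof.

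The cost is two more outputs from the same edited Holter series, two more parameters to report, and slightly more sensitivity to noise from NN editing. No extra visit, device or burden on the child is needed.
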